14.0 STATISTICAL CONSIDERATIONS

Since we do not have any preliminary data for MR imaging, serum biomarkers, etc, it is not feasible to estimate sample size or provide power estimates. Therefore, this study is considered as a pilot study and the data collected will be used to design future studies. We propose six patients each arm as this is considered to be reasonable to recruit within the available a time frame.

In each arm, we will consider the following statistical analysis:

For the primary endpoint, MR imaging will be collected at the time points: pre-MLA (OPTIONAL), post-MLA, two-four weeks after MLA and every twelve weeks in Arm A; pre-MLA, post-MLA, two-four weeks after MLA and every eight weeks in Arm B. The linear regression model will used to investigate the correlation between MR imaging and peritumoral BBB disruption. To account for correlation among the repeated measures from the same patient, the longitudinal data will be analyzed with the use of linear generalized estimating equation (GEE). Whether the average measurements differ at the multiple time points will be evaluated through GEE model. Least-square means at each time points will be presented and standard errors will be calculated within the use of the GEE sandwich method when accounting for within-patient correlation.

Since we do not know which biomarkers will have better correlation with the Ktrans data from DCE and DSC-MRI and patients' survival outcome, we plan to determine the levels of all 3 biomarkers in a blinded fashion. Once both the Ktrans and biomarker levels are available, we will determine which biomarkers have the closest correlation that is statistically significant with the Ktrans. Pearson correlation coefficient (r) will be determined for each biomarker and Ktrans value. Biomarkers with higher correlation coefficient (r approaching 1) will be given higher priority. A minimum $r=0.5$ is required for inclusion for further analysis and will be used as a peritumoral

permeability score. This score will then be correlated with the patient outcome data (as measured by 6PFS rate) to determine whether it has a predictive value.

PFS and OS will be estimated by Kaplan-Meier product limit method. The progression-free survival and overall survival probabilities at certain time points (e.g. 3 months, 6 months) will be presented as well. The difference in OS between Arm A and the historical control of bevacizumab alone will be compared by log-rank test. The quality of life (QOL) using Karnofsky or Lansky performance status will be characterized by summary statistics (mean, standard deviation and range).

The tumor-specific immune responses are collected at pre and post-MLA treatment. Paired t-test will be used to determine the effects of MLA treatment on patient's tumor-specific immune responses. Cox proportional hazard model will be used to determine the relationship between the duration of MLA-induced BBB disruption and PFS.

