1.2 Penetrating the Blood Brain Barrier (BBB)

[figure not shown]
Despite the fact that several cytotoxic and targeted agents have shown significant anti-growth activity in cultured cells, when tested in clinical trials there has been with minimal success, particularly in high grade glioma patients [3, 4]. In one study of pediatric high grade glioma using primary tumor cell cultures, it was shown that several classic chemotherapy agents, including anthracyclines, have a high cytotoxicity in vitro [4]. The high failure rate is in part due to the redundancy in key growth pathways and in drug resistance of malignant cells. Another explanation is the poor CNS penetration many of these drugs have due to the blood brain barrier (BBB). As a result, high doses of drugs were used in studies to achieve therapeutic drug concentrations in the CNS, which led to significant systemic toxicities and limited their clinical usefulness [5]. Preclinical models have shown that the delivery across the blood brain barrier depends on the size and molecular weight of the compound, even after blood brain disruption by mannitol [6]. Thus, an outstanding challenge in neuro-oncology has been to generate drugs that have excellent CNS penetration or methods that can compromise the BBB to enhance drug delivery.

The impact of the BBB on primary brain tumors has been most studied in GBM. GBM typically appear on MR imaging as rim-enhancing masses, suggesting that the BBB within the growth-intensive rim is impaired because contrast enhancement reflects increased BBB permeability [7, 8]. Consequently, delivery of cytotoxic agents to the tumor rim is higher than that to normal brain tissue. However, beyond the enhancing rim – the peritumoral

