1.3.1 Prior Clinical Experience with MLA

We have had one of the largest clinical experiences using MLA in the country. To date we have done more than 80 cases, of which approximately two-thirds are high-grade glial neoplasms. In regards to adverse events, patients have experienced transient aphasia, transient hemiparesis, transient hyponatremia, and a documented case of lower extremity deep venous thrombosis. Patients with aphasia or hemiparesis improved over time with steroid therapy. Hyponatremia resolved spontaneously. One patient experienced fatal meningitis. Subsequent in-depth analysis revealed that this patient's meningitis was due to an operating room infrastructure-related contamination and not due to equipment contamination related to performance of the MLA procedure.

1.4 MLA followed by Standard of Care in Newly Diagnosed Glioma Patients (Arm A)

MLA offers an alternative to some patients with tumors that are unresectable. Complete surgical resection of grade I and II gliomas have a >90% overall survival, although complete resection is not always possible due to the location of the tumor. For tumors with less than a complete resection, chemotherapy or radiation therapy is offered for progressive

and/or symptomatic tumors. For high grade gliomas, patients who have a complete resection of the enhancing tumor at time of diagnosis [29, 30] or at relapse have a longer survival compared to those with residual disease [31]. In this arm of the study, patients with any grade glioma who are candidates for MLA will undergo this procedure followed by standard of care treatment.

1.5 MLA followed by Doxorubicin and Etoposide in Relapsed Malignant Tumor Patients (Arm B)

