3.3 Exclusion Criteria – Arm A

1. Currently receiving or scheduled to receive any other therapies intended to treat the newly diagnosed glioma prior to MLA and the first post-MLA blood collection for correlative studies.
2. Multi-focal or metastatic disease.
3. Pregnant and/or breastfeeding. Premenopausal women must have a negative serum or urine pregnancy test within 14 days of study entry.
4. Inability to undergo MRI due to personal or medical reasons.
5. Known history of HIV or autoimmune diseases requiring immunosuppressant drugs.

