5.0 TREATMENT PLAN

5.1 Study Summary

5.1.1 Arm A

Six patients enrolled to this study will be in Arm A; patients may be enrolled to Arm A at any time throughout the lifetime of the study. Arm A patients will undergo MLA and will be followed with standard of care therapy at the discretion of the treating physician.

Arm A patients will undergo DSC and DCE-MRI at the following time points along with standard of care imaging:

- no more than 3 weeks prior to MLA (OPTIONAL)
- within approximately 4 days after MLA
- 2-4 weeks after MLA
- Every 12 weeks (+/- 7 days) for the first year or until disease progression (see Section 9.1)

Arm A patients will have 7 ml of blood drawn at the following time points:

- Before MLA; this sample can be collected any time during the 3 days before or the day of the procedure until the start of the procedure
- Within approximately 3 days after MLA
- 2-4 weeks (+/- 3 days) after MLA (at time of DSC/DCE-MRI)
- Every 12 weeks (+/- 7 days) at time points correlating with MRIs for the first year or until disease progression

The purpose of these blood draws is to measure serum levels of brain-specific factors (S100B, GFAP, and BSE) and cytokine levels. PBMC (for the pre- and post-MLA samples) will also be isolated to determine the phenotypes and functions of peripheral blood immune cells following MLA (see Section 9.2-9.4).

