12.0 MEASUREMENT OF EFFECT

12.1 Antitumor Effect – Solid Tumors

For the purposes of this study, patients should be re-evaluated for response every 12 weeks on Arm A and every 8 weeks on Arm B. The DCE/DSC-MRI scan obtained within approximately 3 days after MLA will be used as the baseline scan for determining response. The DCE/DSC-MRI scans obtained at pre-MLA, post-MLA, and prior to 6 weeks post-MLA will not be assessed for disease response.

Response and progression will be evaluated in this study using the updated response assessment criteria for high-grade gliomas: Response Assessment in Neuro-Oncology (RANO) working group guideline [JCO 28(11): 1963-1972, 2010].

Criteria for Determining First Progression Depending on Time From Initial Chemoradiotherapy

First Progression	Definition
Progressive disease < 12 weeks after completion of chemoradiotherapy	
Progression can only be defined using diagnostic imaging if there is new enhancement outside of the radiation field (beyond the high-dose region or 80% isodose line) or if there is unequivocal evidence of viable tumor on histopathologic sampling (eg, solid tumor areas [ie, > 70% tumor cell nuclei in areas], high or progressive increase in MIB-1 proliferation index compared with prior biopsy, or evidence for histologic progression or increased anaplasia in tumor). Note: Given the difficulty of differentiating true progression from pseudoprogression, clinical decline alone, in the absence of radiographic or histologic confirmation of progression, will not be sufficient for definition of progressive disease in the first 12 weeks after completion of concurrent chemoradiotherapy.

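### Arm A values from the 2–4 week visit on may mix MLA and standard-therapy effects: the plan reads the time course as MLA-induced, but its analysis ignores when therapy starts

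*Combined protocol and SAP*

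**What the plan says.** Section 3.3, criterion 1, excludes an Arm A patient who is "Currently receiving or scheduled to receive any other therapies intended to treat the newly diagnosed glioma prior to MLA and the first post-MLA blood collection". Section 5.1.1 schedules that draw "Within approximately 3 days after MLA". It also says: "Arm A patients will undergo MLA and will be followed with standard of care therapy at the discretion of the treating physician". Section 1.4 indicates what this therapy can be. When resection is less than complete, "chemotherapy or radiation therapy is offered for progressive" or symptomatic tumours.

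Ktrans and serum markers are measured again at 2–4 weeks, and then every 12 weeks in the first year or until progression (Sections 5.1.1, 9.1 and 9.2).

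For the imaging data, Section 14 plans a GEE model: "Whether the average measurements differ at the multiple time points will be evaluated through GEE model". The biomarkers enter through Pearson correlations with Ktrans. Neither analysis takes account of therapy received.

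**The concern.** The GEE sentence does not itself name MLA as the cause of a change over time. The attribution comes from other sections:

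- Section 1.6 intends to measure how strong, how wide and how long the leakage is after MLA.
- Section 1.7 would read a sharp and persistent biomarker rise as sustained disruption by MLA.
- Section 14 ends with a Cox model relating how long MLA-induced disruption lasts to PFS.

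The protocol itself gives reason to doubt that imaging after other therapy reflects MLA alone. Section 1.2 says that "contrast enhancement reflects increased BBB permeability". The progression table in Section 12.1 restricts imaging-defined progression for 12 weeks after chemoradiotherapy: "Given the difficulty of differentiating true progression from pseudoprogression". That caution is applied to response assessment only, not to Ktrans.

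Secondary objectives 1 and 2 and the Cox analysis are at stake. Section 14 says that the pilot data will be used to design later studies, and the length of the disruption window is a main quantity they would take from it.

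**Working it through.** The plan states no power, effect size or standard deviation for this analysis, so there is no figure to reproduce. The check is a count of visits followed by an illustration.

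**1. Which Arm A visits are protected (first year).** If the 2–4 week visit is at week 2, the 12-weekly visits fall at weeks 14, 26, 38 and 50. If it is at week 4, they fall at weeks 16, 28, 40 and 52. Either way there are four.

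| Visit | Blood | DSC/DCE-MRI | Other therapy excluded? |
|---|---|---|---|
| Pre-MLA | yes | optional | yes |
| About day 3 (blood), day 4 (MRI) | yes | yes | blood yes; MRI not strictly, as the exclusion ends at the draw |
| 2–4 weeks | yes | yes | no |
| Four 12-weekly visits | yes | yes | no |

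Blood: 1 + 1 + 1 + 4 = 7 draws, of which 2 are protected and 5 are not. MRI: 1 + 1 + 4 = 6 required scans. The 1 + 4 = 5 scans from 2–4 weeks on are unprotected. The only scan certain to precede other therapy is the optional one.

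**2. How much of a therapy effect a time-only model takes in (illustration).** Suppose *k* of the 6 patients start therapy before the 2–4 week visit, and therapy shifts a measurement by a constant *d*. Both are assumptions. The mean change from pre-MLA to the 2–4 week visit then contains (*k*/6) × *d*:

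- *k* = 2: 2/6 = 0.33 *d*
- *k* = 3: 3/6 = 0.50 *d*
- *k* = 5: 5/6 = 0.83 *d*
- *k* = 6: 6/6 = 1.00 *d*

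**3. Whether a therapy term could separate the two.** Take 7 categorical visits, a therapy indicator equal to 1 from the 2–4 week visit on in treated patients, and working independence with unit variance.

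- Without the term, the contrast has variance 1/6 + 1/6 = 1/3.
- With it, the variance is 1/3 + (*k*/6)² × 1/[5*k*(6 − *k*)/6].
- *k* = 2: 0.3333 + 0.1111 × 0.1500 = 0.3500; SE ratio √(0.3500/0.3333) = 1.02.
- *k* = 3: 0.3333 + 0.2500 × 0.1333 = 0.3667; SE ratio 1.05.
- *k* = 5: 0.3333 + 0.6944 × 0.2400 = 0.5000; SE ratio 1.22.
- *k* = 6: the design has 8 columns but rank 7, so the therapy effect and the time course cannot be separated.

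Where the term can be estimated, it rests on a constant therapy effect and on comparing six non-randomised patients of differing tumour grade.

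**4. Whether therapy start can be recovered later.** Section 5.9 and footnote 4 of the Arm A calendar name the recording of subsequent treatment only after progression. In Section 11, the Treatment Summary Form is for Arm B only. No listed item calls for the start date of Arm A standard therapy.

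**The case against.** The strongest reply is that the causal link is inferred. No section says that radiotherapy or drugs raise Ktrans, and nothing links S100B, GFAP or BSE to either. This stands, so neither the size nor the direction of any distortion can be stated. A reader might infer that disruption would look falsely long or recurrent; the documents do not support that.

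A reader might also infer that four or five of the six post-MLA scans are contaminated. The visit count shows only that they are unprotected. Assume a 6-week radiotherapy course starting at weeks 3–6, which is not in the documents. It ends on days 63–84. The nominal day-105 scan then lies inside the 12-week window of Section 12.1. The next nominal scan, day 189, is at least 189 − 84 = 105 days (15 weeks) after the end, outside it. At nominal dates the window therefore reaches one scan.

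Therapy is also conditional. Section 1.4 offers it for progressive or symptomatic tumours, and first-year sampling may stop at progression, so therapy prompted by on-study progression would largely come after sampling. Against this, Section 1.1 describes chemoradiotherapy as the current standard for newly diagnosed high-grade glioma, so some early therapy is foreseeable. It does not follow that only high-grade patients would be irradiated: Section 1.4 sets no such limit.

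Finally, Section 11 lists form names, not fields, and the progression rules cannot be applied without chemoradiotherapy dates. Some dates may therefore be collected, but no text secures them for every kind of therapy or carries them into Section 14.

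**Conclusion.** The point holds as a gap in attribution, not as a demonstrated bias. Followed as written, the plan can give an Arm A time course in which MLA and later therapy are not told apart. Five of seven first-year blood draws and all five scans from 2–4 weeks on are open to this. The biomarker change from pre-MLA to about day 3 is not. The quantity most exposed is the duration of disruption, because it depends on the unprotected visits.

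How much this matters depends on how many of the six patients start therapy early, and on whether therapy shifts these measurements at all. The documents give neither. Pilot status lowers the demand for precision but does not remove the need to say what the late values measure.

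Arm B has a related feature by design, since doxorubicin starts 2–14 days after MLA (Section 5.1.2). This point is confined to Arm A, where therapy type and timing are left open.

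**What to change.** - **Follow Up Form (Section 11), Arm A:** add the type and start date of all anti-tumour therapy given after MLA, whether or not progression has occurred.
- **Section 14:** state that Arm A estimates attributed to MLA use only Ktrans and biomarker values obtained before the first such therapy. Apply the same rule to the duration of disruption used in the Cox model, censoring it at therapy start. A duration cut off in this way is only a lower bound and should be listed as such.
- **Later values:** show them per patient with therapy start marked, and describe them as the course after MLA plus standard therapy.
- **Therapy covariate:** do not rely on a time-varying term as the main remedy. With six patients it is descriptive at best, and it cannot be estimated if all start before the 2–4 week visit.

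This takes a few sentences in Section 14 and one addition to an existing form. It adds no visit or procedure and does not alter when therapy may start. The price is fewer Arm A values in the MLA estimate. Later pre-therapy values will come only from patients not yet treated, which is a selected group. In patients who start therapy early, duration may not be estimable, and the report should say so.

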2.0 OBJECTIVES

2.1 Primary Objectives

1. To determine progression-free survival (PFS) and overall survival (OS) of patients with new diagnosis glioma who are candidates for MLA (Arm A).
2. To determine 6-month progression-free survival (6PFS) in patients who receive doxorubicin immediately following MLA and low-dose etoposide as maintenance therapy in patients who are candidates for MLA with any type relapsed malignant brain tumors (Arm B).
3. To evaluate quality of life (QOL) using Karnofsky or Lansky performance status in patients following MLA and in patients who receive doxorubicin and maintenance etoposide after MLA.

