5.1.2 Arm B

Six patients enrolled to this study will be in Arm B; patients may be enrolled to Arm B at any time throughout the lifetime of the study. Arm B patients will undergo MLA and will begin doxorubicin (as described in Section 5.4) within approximately 7 days following MLA (range 2-14 days)

Arm B patients will undergo DSC and DCE-MRI at the following time points along with standard of care imaging:

- no more than 3 weeks prior to MLA (OPTIONAL)
- within approximately 4 days after MLA
- 2-4 weeks after MLA
- every 8 weeks (+/- 7 days) until 2 years have elapsed or disease progression (see Section 9.1), whichever comes first

Arm B patients will have 7 mL blood drawn at the following time points:

- before MLA; this sample can be collected any time during the 3 days before or the day of the procedure until the start of the procedure
- within approximately 3 days after MLA
- weekly (+/- 3 days) before (on the same day as) chemotherapy for the 6 weeks post-MLA
- every 8 weeks (+/- 7 days) at time points correlating with MRIs for the first 2 years or until disease progression, whichever comes first

The purpose of these blood draws is to measure serum levels of brain-specific factors (S100B, GFAP, and BSE) and cytokine levels. PBMC (for the pre- and post-MLA samples) will also be isolated to determine the phenotypes and functions of peripheral blood immune cells following MLA (see Section 9.2 -9.4). This is in addition to blood samples for routine laboratory prior to chemotherapy and surgery. During the weeks of DSC/DCE-MRI, biomarker lab must be drawn on the same day as DSC/DCE-MRI (prior to the scan).

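### Section 14 calls repeated MR imaging primary against Section 2, and its six-patient GEE understates standard errors by about 9% and leaves the test over time undefined

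*Combined protocol and SAP*

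**What the plan says.** Section 14 introduces its methods with "In each arm, we will consider the following statistical analysis" and then writes "For the primary endpoint, MR imaging will be collected at the time points". It specifies a linear GEE for the repeated imaging measurements: "Whether the average measurements differ at the multiple time points will be evaluated through GEE model". On the variance, the text is that "standard errors will be calculated within the use of the GEE sandwich method when accounting for within-patient correlation". What will be reported from the model is given as "Least-square means at each time points will be presented". The sample is six patients per arm, chosen on recruitment grounds, with no power calculation. The section names no small-sample correction, working correlation, test type, reference distribution or significance level for this model.

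Section 2.1 lists different primary objectives. The first begins "To determine progression-free survival (PFS) and overall survival (OS) of patients with new diagnosis glioma" (Arm A); the others are 6-month PFS (Arm B) and performance status as quality of life. Imaging correlates of barrier disruption are the first secondary objective in Section 2.2.

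Section 14 gives the Arm B imaging times as "pre-MLA, post-MLA, two-four weeks after MLA and every eight weeks in Arm B" and marks the pre-MLA scan optional only for Arm A. Section 5.1.2 lists the same Arm B scan as "no more than 3 weeks prior to MLA (OPTIONAL". Section 9.1 and the Arm B calendar in Section 10.2 also make it optional.

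**The concern.** Two things are at stake. First, the document has two different sets of primary endpoints. Section 1.3 adds to the doubt by describing barrier disruption after MLA as the study's main focus, so a reader cannot tell which designation governs reporting.

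Second, the sandwich variance is justified for many independent clusters, and here each model has six. Left uncorrected it is biased downward, and the usual large-sample tests built on it are unreliable. Section 14 says the data will be used to design later studies, so understated standard errors or a spurious (or missed) change in imaging over time would carry into that planning. The bias grows at later visits, because scans stop at progression (Sections 5.1.1, 5.1.2 and 9.1) and fewer patients contribute.

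**Working it through.** There is no sample-size formula or power figure to reproduce, so the check is on how the stated analysis behaves.

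**Inputs.** Six patients per model (Section 14: six per arm, analysed by arm). Time is treated as categorical, which the plan's least-square mean at each time point supports. Assumed, because the plan does not give them: two-sided 5% level, normal errors and, except where stated, complete data.

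**Endpoint label.** Section 14 attaches the word primary to MR measurements and analyses them by GEE. PFS and OS are handled separately later in the same section, by Kaplan-Meier. Section 12.1 says the pre-MLA, post-MLA and pre-6-week scans are not used to judge response, yet pre-MLA, post-MLA and 2-4 week scans head the Section 14 list. The label therefore cannot mean only that MRI supplies the PFS assessments.

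**Standard error of a visit mean.** With residuals r and n patients, the uncorrected sandwich variance is Σr²/n²; the usual variance is Σr²/[n(n−1)]. The SE ratio is sqrt((n−1)/n):

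| Patients at visit | SE ratio |
|---|---|
| 6 | 0.913 |
| 4 | 0.866 |
| 3 | 0.816 |

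The rows for 4 and 3 assume an independence working correlation. This result needs no significance level or reference distribution.

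**One contrast between two visits, six patients.** Let t be the ordinary paired t statistic on 5 df.

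- Wald with z reference: P(|t₅| > 1.96 × 0.913) = 13.4%. A check with 1,500 fitted GEEs gave 13.7%.
- Same SE with t(5) reference: P(|t₅| > 2.571 × 0.913) = 6.6%.
- Generalized score test: the statistic is 6t²/(t² + 5). It exceeds 3.84 when t² > 5 × 3.84/(6 − 3.84) = 8.90, so |t₅| > 2.98 and the size is 3.1%.

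**Joint test that all visit means are equal, p = time points − 1.** The uncorrected Wald chi-square test rejects when Hotelling's T² > χ²₀.₉₅(p) × 5/6, and T²(6−p)/(5p) follows F(p, 6−p):

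| Time points | p | True size |
|---|---|---|
| 3 | 2 | 25% |
| 4 | 3 | 42% |
| 5 | 4 | 62% |
| 6 | 5 | 84% |

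The joint score statistic cannot exceed 6. Its cutoff is 5.99 at p = 2, so rejection is almost impossible, and 7.81 at p = 3, so rejection is impossible from there on.

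**Rank.** The six patients' contributions to the robust covariance sum to zero, so its rank is at most 5. Seven time points need six contrasts, and the joint Wald test is then singular. Arm A has six scheduled first-year scans (for example weeks 0, 3, 15, 27, 39, 51), or seven with the optional pre-MLA scan. Arm B, every 8 weeks for two years, has about 14 to 16; its seventh post-MLA scan falls at about week 42-44.

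**The case against.** The strongest objection is that the plan never says it will use a Wald test with a normal or chi-square reference. A reader might infer from the 13.4% and 84% figures that the plan, as written, guarantees a false-positive rate well above 5%. The documents do not support that: the same standard error with t(5) gives 6.6%, and a score test is conservative. This objection stands. What remains is that the choice is open and that size with six patients depends heavily on it.

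A reader might also say that the planned confidence intervals are too narrow. Section 14 promises least-square means and standard errors, not intervals, so only the understated standard error follows from the text. Nor can a particular error rate be put on later visits: that would need a dropout pattern the documents do not give.

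On the optional scan, three other places agree that it is optional in Arm B, so the omission in Section 14 is editorial. It would also be too strong to call pre- versus post-MLA the only comparison that bears on disruption. Sections 1.6 and 1.9 describe post-procedure Ktrans followed over time and returning to a low baseline, so later scans are informative too.

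Finally, this is a declared pilot without power, and no decision rule rests on an imaging p-value. That limits the severity but does not remove the point: the plan commits to standard errors and to a test, and both feed future designs.

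**Conclusion.** The point holds in this form. The primary-endpoint label in Section 14 contradicts Section 2, and the documents do not settle which is meant. If the named sandwich method is used without correction, every visit-mean standard error is about 9% low with six complete patients, and 13% or 18% low with four or three under independence working correlation. The test over time is not defined well enough to have a known size. Under ordinary choices it runs from 3.1% to 13.4% for one contrast, and from almost zero to 84% jointly at up to six time points. A joint Wald test cannot be carried out over the full Arm B schedule.

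The standard-error result with six patients rests on categorical time and complete data. The size figures also assume normal errors and a two-sided 5% level. The amendment should be made, but no confirmatory conclusion is at risk.

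**What to change.** - Reconcile Sections 2 and 14. If Section 2 governs, Section 14 should refer to the imaging secondary objective; if imaging is meant to be primary, Section 2 must say so.
- Name peritumoral Ktrans as the longitudinal outcome.
- Replace the all-time-point test with one prespecified main contrast, pre- versus post-MLA, among patients who have the optional scan. Use paired differences with a t reference on (pairs − 1) df, or GEE with a Mancl-DeRouen correction and the same t reference. With six pairs, simulated size is 5.0% and 3.7% respectively. The correction with a z reference still gave 8.3%, so both the correction and the reference must be named. Section 14 already uses a paired t-test for the immune data.
- Present all other visits, including those bearing on recovery and duration, as exploratory estimates with small-sample-corrected standard errors, t intervals and the number of patients per visit.
- If a second contrast is tested, adjust for multiplicity or label it exploratory. Two paired t contrasts sharing the post-MLA scan have a 9.4% chance of at least one false positive. Post-MLA versus 2-4 weeks should not be described as establishing duration, because both scans fall inside the 6-week window that Section 1.5 assumes.
- State in Section 14 that the Arm B pre-MLA scan is optional, as the other sections do.

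The cost is wording and fewer p-values; no new data are needed. A t(5) interval is 2.571/(1.96 × 0.913) = 1.44 times as wide as an uncorrected normal one. The 95% half-width of the paired contrast, t/sqrt(pairs), is 1.05 SD of the within-patient differences with 6 pairs, 1.59 with 4 and 2.48 with 3, so the contrast is informative only if most patients have the optional scan.
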